### **1.5.2 Specific Objectives**

This study aimed to evaluate a KC-EP supporting KC among mother-infant dyads and nurses.

The specific objectives of this study were to:

1. compare the effectiveness of KC-EP in terms of mothers' perception, knowledge, and perceived barriers regarding KC and their level of stress after participation in a KC-EP between control and experimental groups of mothers at T0, T1 and T2.
2. compare premature infants' weight gain patterns, LOS and breastfeeding rates between control and experimental groups at T0, T1, and T2.

3. compare nurses' perception, knowledge, and practice of KC before and after participation in a KC-EP for nurses.

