## **1.6 Hypothesis**

The following hypotheses guided the study:

- $H_1$ : A KC-EP can improve perception, knowledge, and perceived barriers in relation to KC, and levels of stress among mothers.
- $H_2$ : KC is effective in improving weight gain patterns, LOS, and breastfeeding rates among premature infants.
- $H_3$ : A KC-EP can improve nurses' perception, knowledge, and practice in relation to KC implementation.

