### **3.3 Study Design**

This is a quasi-experimental(QED), longitudinal design study to collect data on the effectiveness of a kangaroo care education programme (KC-EP) for mothers', nurses' and infants' outcomes. The QED is often described as a non-randomized, pre-post intervention study that is common in healthcare research when it is not logistically practicable or ethical to carry out a randomized control trial (Levin & Kate, 2007). This study met all four criteria of Harris, McGregor, Perencevich, Furuno, Zhu, Peterson, & Finkelstein (2006). Each reason is discussed below. In a human study, randomization in the intervention of known efficacy would not be allowed, unless the effectiveness is not known or doubtful. According to Jotzo, Martina & Christian (2005), psychological and mental support is required in critical circumstances, i.e. after premature birth. In the emotionally sensitive NICU environment, it seems unethical to provide some mothers with help, but other people oppose randomization for other reasons. A QED is an empirical instrument used to measure the causal effect of an

intervention on the basis of longitudinal evidence to decide whether the intervention has led to improvements in the outcomes of the target population. This study evaluated the effect of an educational programme on the outcomes of mothers, nurses, and preterm infants regarding KC techniques.

A QED design is considered an adequate technique for evaluating the causal and successful relationship between the independent and dependent variables found when a fully experimental or randomized control trial (RCT) design is not feasible (Harris et al., 2006). RCT is also not realistic for research into small-scale continuing education. Due to the aspect of non-random assignment to the control group or experimental group, a quasi-experimental research design was chosen as a multilevel intervention for the preterm infant. The experimental group participated in a structured training programme on evidence-based experience and skills: a KC-EP for mothers and nurses. The mother-infants dyad in the control group followed the standard unit practice, and both groups had homogeneous or similar characteristics.

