### **3.19.1 Analysis of Quantitative Data**

Graduate Package 23.0 of the Statistical Package for Social Sciences (SPSS) provided tools to analyze the data required to achieve the research objectives:

In the pretest of dependent variables, data from the mothers and infants were evaluated for homogeneity, normality, variability, and data normality in the pretest. Nevertheless, the variance test for the nurses' data was not homogeneous since we were dealing with the same group, the data were normally distributed and the variances between the groups were equal, and the sample size was acceptable (no less than 30 cases per group). The number and proportion were stated as continuous variables and categorical variables. Continuous variables were compared for normally distributed variables ('mothers' and 'infants') using the independent t-test and variance analysis (ANOVA/ANCOVA). Pearson's chi-square test was used because the independent variables were nominal categorical variables. The Chi-square test was applied with normally distributed data to establish associations between independent variables, such as age, years of service as RN, years of working in NICU and educational qualification level, and dependent variables: perception, knowledge and outcomes improvement: weight gain, length of hospitalization stay and breastfeeding rates. In addition, the Shapiro-Wilk test was used to test data normality for both the pre and post-test, as the sample was below 50 per arm. To assess the effect of the structured kangaroo care educational program (KC-EP) on mothers', infants' and nurses' outcomes, for the data on mothers, infants and nurses, the general linear model (GLM) univariate analysis of variance and covariance analysis was used. GLM and repeated measures were used to analyze the main effects and interaction effects of KC outcome variables, and to examine the hypotheses of the outcomes.

Table 3.4: Summary of Statistical Analysis of Quantitative Data Plan

No.	Objectives	Measurement Variables	Statistical analysis

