1.	Are there any statistically significant differences in mothers' perception, knowledge, perceived barriers regarding KC, and stress related to 'premature infants admission to NICU' after participation in the KC-EP?	Perception, knowledge, perceived barriers and stress related to premature infants' admission to NICU mean scores Effect of KC-EP KC performance (Ordinal data)	Descriptive - mean, SD, skewness and kurtosis Chi-square test, GLM, repeated measure (RM) & Pearson Eta Squared.
2.	Does kangaroo care improve weight gain patterns in premature infants between control and experimental groups at $T_0$ , $T_1$ , and $T_2$ ?	Weight gain patterns (grams) mean score KC compliance Duration (hours/weeks) Frequency and Percentage (Continuous data)	Descriptive – mean, SD, skewness and kurtosis Chi-square test, GLM and t-test.
3.	Does kangaroo care decrease the length of hospitalization stay for premature infants between control and experimental groups?	Length of hospitalization stay Frequency and percentage (Continuous data)	Descriptive – mean, SD, skewness and kurtosis Chi-square test, GLM and test
4.	Does kangaroo care improve breastfeeding rates for premature infants between control and experimental groups?	Breastfeeding rates KC compliance Frequency and percentage (Continuous data)	Descriptive – mean, SD, skewness and kurtosis Chi-square test, GLM and t-test.
5.	Are there any statistically significant differences in nurses' perception, knowledge, and practice regarding KC before and after participation in the KC-EP?	Perception, knowledge, practice mean scores Effect of KC-EP (Ordinal data)	Descriptive - mean, SD, skewness and kurtosis Independent t-test GLM, RM & Pearson Eta Squared.

The key influence of an explanatory variable is its direct effect on the outcome variables (Field, 2011). Additionally, the effects of covariate and covariate interaction with KC can be included in GLM univariate analysis. This covariance analysis is an extension of the variance analysis to include a covariate/confounder component (Field, 2011). This covariance is linearly related to the dependent variable, and its inclusion in the analysis will minimize the error associated with the covariance analysis (Field, 2011). The test is appropriate since

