categorical variables are both independent and dependent variables. Therefore, covariance analysis was used to correct the observed effects on the outcome variables of potential confounders. The summary of the statistical analysis used for all research questions is outlined in Table 3.14. Each of the statistical tests is two-tailed. A p-value below 0.05 was assumed to show statistical significance.

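### The plan does not say which repeated-measures term decides H1, and it admits a group main effect that includes the pre-programme T0 score

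*Combined protocol and SAP*

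**What the plan says.** H1 in section 1.6 reads: "A KC-EP can improve perception, knowledge, and perceived barriers in relation to KC, and levels of stress among mothers". Objective 1 in section 1.5.2 compares four scores, including "level of stress after participation in a KC-EP between control and experimental groups of mothers", at T0, T1 and T2.

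Section 3.19.1 describes two analyses. To assess the effect of the programme, "the general linear model (GLM) univariate analysis of variance and covariance analysis was used". It then adds that "GLM and repeated measures were used to analyze the main effects and interaction effects of KC outcome variables, and to examine the hypotheses". For the mothers' scores, Table 3.4 row 1 lists "Chi-square test, GLM, repeated measure (RM) & Pearson Eta Squared" and names no term or contrast. After the table, the text says that "covariance analysis was used to correct the observed effects on the outcome variables of potential confounders", without listing the covariates. The only decision rule is a two-sided p-value below 0.05.

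On design, section 3.16.2 places the T0 questionnaire before the programme, and section 3.16.3 has the scores measured at T0, T1 and T2. Section 3.6 describes non-random recruitment by admission day. Section 3.16 has the control phase in February to July 2018 and the experimental phase in October 2018 to April 2019, after the nurses were trained. Section 3.3 states that "both groups had homogeneous or similar characteristics". Section 3.19.1 says the pretest data were evaluated for homogeneity, but gives no rule for what follows if the groups differ.

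**The concern.** A repeated-measures GLM on two groups and three visits gives three tests: group, time, and group by time. The plan admits main effects and interactions alike for examining the hypotheses and does not choose among them. Any of the three falling below 0.05 could be reported as support for H1.

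Two of the three do not test H1. The group main effect compares averages over all three visits, and one of those visits precedes the programme. The time main effect shows change averaged over both groups, which would include ordinary adaptation as the infant recovers and goes home.

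A starting difference is a real possibility here. The groups come from different months, and the nurses were trained between them. Experimental mothers had to be willing to perform kangaroo care (section 3.16.2), whereas control mothers practised it only if interested (section 3.16.1). Four conclusions depend on the choice of term: perception, knowledge, perceived barriers and stress.

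**Working it through.** **The plan's own figure.** The documents give no effect size, SD or correlation for the mothers' scores. The only sample-size calculation (section 3.7.2) concerns infant weight gain. It reproduces: 2 × 2.802² × 0.64 / 0.29 = 34.65, so 35 per group, and 35 / 0.7 = 50 after the 30% allowance. It gives no input for H1.

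**Inputs from the documents.** 48 per group (section 3.7.2), three visits with T0 before the programme, two-sided 0.05.

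**Assumptions, not in the documents.** Scores scaled to SD 1 at each visit; equal correlation r between visits, taken as 0.3, 0.5 and 0.7; a starting difference b that persists at all visits; a programme effect d that is the same at T1 and T2. Normal approximation throughout.

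**What each term estimates.**
- Group main effect: (b + (b + d) + (b + d)) / 3 = b + (2/3)d.
- Group-by-time contrast, mean of T1 and T2 minus T0: (b + d) − b = d.
- Mean of T1 and T2 adjusted for T0: (b + d) − r·b = d + (1 − r)b.

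**Variance per mother.**
- Mean of three visits: (1 + 2r)/3 = 0.533, 0.667, 0.800.
- Contrast: (1 + r)/2 + 1 − 2r = 1.05, 0.75, 0.45.
- T0-adjusted: (1 + r)/2 − r² = 0.56, 0.50, 0.36.

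The standard error of a group difference is √(2 × variance / 48). Worked case for the group main effect at r = 0.5 and b = 0.3: SE = √(2 × 0.667 / 48) = 0.167, z = 0.3 / 0.167 = 1.80, and the chance of exceeding ±1.96 is 44%.

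**Rejection rate with no programme effect and a lasting 0.3 SD gap**

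| Test | r = 0.3 | r = 0.5 | r = 0.7 |
|---|---|---|---|
| Group main effect | 52% | 44% | 38% |
| Contrast (T1/T2 mean minus T0) | 5% | 5% | 5% |
| T0-adjusted difference | 28% | 18% | 11% |

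At r = 0.5 the group main effect rejects 22% of the time for a 0.2 SD gap and 85% for a 0.5 SD gap. In simulation (4,000 runs per setting) the ordinary interaction F test stayed at about 5% at 0.3 SD.

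**Power with level groups and a true 0.5 SD effect** (the main effect sees 2/3 × 0.5 = 0.33 SD)

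| Test | r = 0.3 | r = 0.5 | r = 0.7 |
|---|---|---|---|
| Group main effect | 61% | 52% | 45% |
| Contrast | 67% | 81% | 95% |
| T0-adjusted difference | 91% | 93% | 98% |

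The loss against the contrast is 6 percentage points at r = 0.3, 29 at 0.5 and 50 at 0.7.

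**The case against.** A reader might infer that the plan tests H1 by the group main effect, and so treats starting differences as programme effects by design. The documents do not support that. The sentence that names main effects also names interaction effects, and in this design the interaction of interest is group by time. The sentence before it assigns the programme effect to univariate analysis of variance and covariance, with covariance analysis meant to correct for confounders. Objective 1 can equally be read as a comparison at each visit. The defect is that an unsuitable term is admitted alongside a suitable one and nothing decides between them.

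Two further objections stand in part. First, the power argument depends on an unknown correlation. At r = 0.3 the loss against the contrast is small, and the ordinary two-degree-of-freedom interaction test has about 55% power for a 0.5 SD effect, below the main effect's 61%. Dilution by a third is certain, but a weaker test is not. Second, neither alternative is free of assumptions. The contrast is valid only if the groups would otherwise have changed in parallel, and T0 adjustment leaves part of a lasting gap in place.

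The objection does not remove the problem. Naming the interaction does not exclude the main effects as tests of the same hypothesis. The covariance analysis does not name T0 as a covariate or restrict the outcome to T1 and T2. The pretest homogeneity check leads to no stated action.

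**Conclusion.** The concern holds as an unspecified deciding term that leaves an unsuitable test admissible for H1. Followed as written, the plan lets a group main effect containing the pre-programme score, or a time effect pooled over both groups, count as evidence that the programme worked. With a lasting gap of 0.3 SD and no effect, the group main effect would be significant 38% to 52% of the time against a nominal 5%, for correlations of 0.7 down to 0.3. The b + (2/3)d result needs only three equally weighted visits, a gap that persists and an equal effect at T1 and T2. The percentages also rest on 48 complete mothers per group, equal variances and equal correlations. The size of any actual T0 gap is unknown, so these figures show what the wording allows and do not predict the result. The false-positive risk is the main reason to act; the power loss is secondary and small at low correlation.

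**What to change.** In section 3.19.1 and Table 3.4 row 1, state that:

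1. H1 is decided separately for perception, knowledge, perceived barriers and stress by the group-by-time contrast, the mean of T1 and T2 minus T0.
2. The group and time main effects are descriptive and are not evidence for H1.
3. The contrast assumes that, without the programme, the two groups would have changed in parallel from T0.
4. Group differences at T1 and T2 adjusted for T0, with 95% confidence intervals, may be reported as supportive only, noting that they do not fully remove a lasting baseline gap (28%, 18% and 11% rejection at 0.3 SD for correlations of 0.3, 0.5 and 0.7).

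This costs a few sentences of analysis text and a specified contrast on scores already collected at three visits. The T0-adjusted estimates are one further analysis of the same data. No new data or larger sample is needed.

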### **1.7.12 Breastfeeding rates**

Breastfeeding is the method of providing nutrients that are essential for healthy growth and development to young infants, according to WHO (2020). Colostrum is the sticky, yellowish breast milk formed at the end of pregnancy and is accepted as the perfect nutrition for the newborn; feeding begins within the first hour of birth. In this study, breastfeeding rate refers to the rate preterm infants started breastfeeding or taking EBM, partially or exclusively, starting from 29 weeks, and continued breastfeeding along with appropriate formula milk for the first 3 months and beyond or were weaned at a certain week of gestation.

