#### **2.4.4 Kangaroo Care Studies and Breastfeeding**

An observational study carried out by Singh, Amritanshu & Mukherjee (2014) in the Department of Community Medicine at Katihar Medical College's Department of Pediatrics, among 100 infants with weights ranging from 1650 grams to 2000 grams, concluded that KC's other benefits are that it encourages exclusive breastfeeding and enhances the confidence of mothers in holding their small infants.

A further research on the beneficial impact of KC on breastfeeding was also conducted in Central India from November 2012 to September 2013 over an 11-month period. The researchers reported that breastfeeding was established in the KC group at 68.5%, as well as in the discharge control group at 34.2%, favoring the KC group ( $p<0.05$ ). In addition to this, it was found that exclusive breastfeeding was more prevalent in the KC group than in the control group. The proportion of breastfeeding preterm infants was greater at 40 weeks (KC: 94.4%; control: 72.0%  $p<0.002$ ), three months (KC: 89.6%; control: 62.2%  $p<0.002$ ), and six months (KC: 84.6%; control: 55.5%  $p<0.006$ ) post-conception age, the difference being statistically significant.

Breastfeeding Policy (NBP) in Malaysia suggests exclusive breastfeeding for the first six months and then continued breastfeeding for up to two years. Several programs to encourage breastfeeding have been introduced in this country since the 1990s. In response to assess the frequency of breastfeeding practice, a maximum of 2167 mothers or caregivers of children

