***b) Section B: Infant's Kangaroo Care Progress Record (KCPR) or Data Sheet***

Section B assessed the progress of the premature infant in terms of primary and secondary outcomes. The primary outcome variables were weight gain and LOS, while the secondary outcomes were breastfeeding rate or feeding status. All nine (9) items were adapted from the original article by Singh, Amritanshu and Mukherjee, (2014) and Biswas, Malpani & Ekka, (2016) with a slight modification and format to satisfy the research goals relevant to the main and secondary monitoring requirements of the use of KC to assess outcomes. The variables consisted of baseline temperature, age of KC initiation (week/days), weight at KC initiation (g/days), weight gain velocity (g/days), duration of KC (in hour/day), duration of stay (days), types of milk (EBM or breastfeeding), initiation of breastfeeding (weeks) and weaning from breastfeeding (weeks) for both groups. The KCPR booklet was designed and presented to the

respective control and experimental groups. The difference in the KCPR booklet was the knowledge needed for the experimental group to get the input given to the control group for preterm infants (routine activities and standard care) and KC performance. The data for the preterm infants in the control group were documented according to standard practice care or routine practice in the NICU. [Please refer to Appendix F(a) and F(b)].

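### The secondary outcome of breastfeeding rates is not tied to one variable, is labelled continuous, and has no rule for infants still breastfed at T2

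*Combined protocol and SAP*

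**What the plan says.** Breastfeeding is ranked below weight gain and length of stay: "while the secondary outcomes were breastfeeding rate or feeding status" (section 3.9, part b). The infant objective in section 1.5.2 is to "compare premature infants' weight gain patterns, LOS and breastfeeding rates between control and experimental groups at" T0, T1 and T2.

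The operational definition in section 1.7.12 has two parts. First, "breastfeeding rate refers to the rate preterm infants started breastfeeding or taking EBM, partially or exclusively, starting from 29 weeks". Second, that the infants "continued breastfeeding along with appropriate formula milk for the first 3 months and beyond or were weaned at a certain week of gestation".

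The recorded variables differ by place:
- Section 3.9, part b lists initiation in weeks and "weaning from breastfeeding (weeks) for both groups"; part a gives weaning as week/month.
- Item 10 of the infant form (Appendix F(a) and F(b), Part I) asks for the month of weaning from exclusive breastfeeding.
- Section 3.16.2 says breastfeeding status was collected in weeks from T0 to T2.

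In Table 3.4, row 4 reads "Breastfeeding rates KC compliance Frequency and percentage (Continuous data", with the descriptives and tests of a continuous variable plus chi-square. The text after the table calls both independent and dependent variables categorical. Earlier in section 3.19.1, continuous infant variables go to the independent t-test and ANOVA/ANCOVA, the effect of the programme goes to the general linear model, and chi-square is described for associations with participant characteristics. Follow-up ends at 3 months. Section 3.16.4 a) lists type of milk and the weeks breastfeeding started and stopped as confounding variables.

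**The concern.** Initiation, current status and duration are different quantities, and each needs its own analysis. The plan names one rate, gives it the scale of a duration, and lists tests for both. An analyst following the continuous label would compare mean weeks.

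That is where harm could arise. Weaning week is unknown for every infant still breastfed when follow-up stops. Dropping those infants discards the ones with the best outcome, and discards more of them from the group that does better. Giving them the T2 week is a different analysis with a different answer. The plan chooses neither and has no time-to-event method.

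The choice between any and exclusive breastfeeding matters too. The two can sit at opposite ends of the scale, and what 48 infants per group can detect changes accordingly.

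**Working it through.** **The plan's own sample size.** Section 3.7.2 sizes the study on weight gain: 2 × (1.96 + 0.842)² × 0.8² / 0.54² = 34.5, so 35 per group, and 35 / (1 − 0.30) = 50. This reproduces. Nothing is stated for breastfeeding, so the rates below are assumptions taken from studies cited in the protocol. They are not planning values. The group size used is 48 per arm, with two-sided alpha of 0.05.

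**1. Who would have a weaning week.** One study cited in section 2.4.4 reports "three months (KC: 89.6%; control: 62.2"%. If those were the proportions still breastfed at T2:
- experimental: 48 × (1 − 0.896) = 5.0 observed
- control: 48 × (1 − 0.622) = 18.1 observed

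The same study's other time points give a range: 2.7 and 13.4 (94.4% and 72.0%), or 7.4 and 21.4 (84.6% and 55.5%).

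If the item analysed were instead weaning from exclusive breastfeeding, the cited survey rates of 29% at 4 months and 14.5% under 6 months would give 48 × 0.71 = 34 to 48 × 0.855 = 41 observed. Censoring would then be modest.

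**2. Effect of the handling rule.** Assume constant weaning hazards, with T2 taken as 13 weeks:
- control: λ = −ln(0.622)/13 = 0.0365 per week
- experimental: λ = −ln(0.896)/13 = 0.0084 per week
- hazard ratio 0.23

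With S the proportion still breastfed at 13 weeks, the mean week among weaned infants is 1/λ − 13S/(1 − S):
- control: 27.38 − 21.39 = 5.99
- experimental: 118.38 − 112.00 = 6.38

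The observed weeks are almost the same although the hazards differ more than fourfold. Over 2,000 simulated trials (simulation error below 0.01):

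| Handling of infants still breastfed at T2 | Power |
|---|---|
| t-test, infants dropped | 0.05 |
| t-test, infants set to 13 weeks | 0.82 |
| log-rank, infants censored | 0.90 |

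**3. Yes/no status at T2.** For 62.2% against 89.6%, the pooled proportion is 0.759. The null standard error is √(2 × 0.759 × 0.241/48) = 0.0873. The alternative standard error is √((0.622 × 0.378 + 0.896 × 0.104)/48) = 0.0827. Then (0.274 − 1.96 × 0.0873)/0.0827 = 1.24, a power of 0.89.

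Over 20,000 simulated trials per scenario, a t-test on 0/1 status agreed with chi-square in at least 99.7% of trials, with type I error of 0.045 to 0.052.

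**4. Any or exclusive.** By the same formula, a control rate of 94.7% (the any-breastfeeding survey figure in section 1.1.3) gives power of 0.36 even against almost 100%. For exclusive feeding, 14.5% against 40% gives 0.81.

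**The case against.** Row 4 does list chi-square, which suits a yes/no status, and a t-test on 0/1 data does little harm at this sample size. The measure is given as frequency and percentage, which points to status. Nowhere does the plan say that weaning week is the tested variable or that infants still breastfed are dropped. The row 4 cell also contains KC compliance, which is a duration in row 2, so the continuous label may belong to that; the extracted table cannot settle it. All of this stands, and it makes the loss of power conditional. It does not remove the ambiguity. The definition includes weaning week, several sections record breastfeeding in weeks, and section 3.19.1 sends continuous infant outcomes to mean-based methods.

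A reader might infer that counting formula-supplemented feeding as breastfeeding means the comparison misses the stated objective. The documents do not support that. The objective says breastfeeding rates, the definition openly covers partial feeding, the mothers' module aims at partial or exclusive breastfeeding, and section 1.3 f) places exclusive-breastfeeding assessment at six months in future research. The consequence is narrower: the merged rate cannot support a statement about exclusive breastfeeding. Making exclusive breastfeeding the endpoint would be a preference.

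The 89.6% and 62.2% come from one cited study. They follow a sentence on exclusive breastfeeding, so even their definition is uncertain.

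**Conclusion.** The point holds as a problem of definition, scale and handling for one secondary outcome. Initiation, status and duration share one name. The units and the weaning event differ between places. The continuous label conflicts with the frequency measure and with the later statement that dependent variables are categorical. Infants still breastfed at T2 have no rule.

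If status is compared as proportions, the damage is small. If weaning weeks are compared by t-test or GLM with those infants dropped, nearly all power could go (0.05 against 0.90). That figure assumes constant weaning hazards, a 13-week cut-off and the borrowed 3-month rates. Censoring is inferred from the end of follow-up; the documents do not discuss it. It would be wrong to conclude that the plan commits to the damaging analysis. It leaves that analysis open and makes it a natural reading.

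**What to change.** Change row 4 of Table 3.4 and the matching text of section 3.19.1 as follows:
- Relabel breastfeeding as categorical, and separate it from KC compliance.
- Name any breastfeeding (yes/no) at T2 as the tested variable, in line with section 1.7.12. Report exclusive, partial and none at discharge, T1 and T2 where the booklet allows.
- Compare groups by chi-square or logistic regression, with a risk difference and 95% CI. Remove the mean, SD and t-test for this outcome.
- If weaning is analysed, state whether the event is the end of any or of exclusive breastfeeding, and use one unit. Use Kaplan-Meier and log-rank, with infants still breastfed censored at last contact.
- Do not adjust this outcome for type of milk or breastfeeding duration. They are parts of the outcome, although section 3.16.4 a) lists them as confounders.

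The cost is a little extra analysis work and no new data item for any-breastfeeding status. Exclusive status at T2 is less certain. The sample diary in Appendix O(a) has separate boxes for expressed milk, breastfeeding and formula. The data sheet in Appendix F(b) has no formula option and runs only to discharge. Exclusive status therefore depends on how completely the booklet was filled in at home.
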